Acute kidney injury is defined as the abrupt onset of renal dysfunction resulting from injurious endogenous or exogenous processes characterized by decrease in GFR and increase in serum creatinine. AKI leads to the inability to regulate acid and electrolyte balance and the inability to excrete waste and fluid. The exact incidence of AKI is unknown due to the heterogeneity of definitions of AKI reported in the literature. Recently, the pRIFLE criteria were developed to aid in the definition and classification of AKI in children (6).

In a heterogeneous group of about 3400 critically ill children in a tertiary PICU, [name] et al. (Principal Investigator) identified AKI in about 10% of patients (2). AKI was found to be independently associated with prolonged PICU length of stay as well as length of mechanical ventilation. Further, AKI was independently associated with mortality, worsening with increasing degree of AKI.

Acute kidney injury is a common complication after cardiac surgery under cardiopulmonary bypass. In a retrospective chart review of 458 pediatric (<18 years of age) patients undergoing corrective surgery for congenital heart defects at Cohen Children's Medical Center of New York between 2006 and 2009, we demonstrated that 51% of patients developed AKI during their postoperative stay in the pediatric intensive care

unit. The incidence was even greater when limiting the analysis to neonates (<30 days of life), where 60% of patients developed AKI postoperatively (7). Li, et al, have also shown in a prospective multicenter analysis of children undergoing congenital heart corrective surgery that the incidence of AKI is 42%, but significantly higher in patients <2 years of age (8). AKI was identified as an independent risk factor for prolonged ICU and hospital length of stay as well as prolonged mechanical ventilation (7,8). To date, though, no study has identified a particular intervention or series of interventions (bundles) that can limit the development of this independent risk factor for poor outcomes in children undergoing CPB for corrective heart surgery. Pilot and laboratory data suggest that continuous infusion of sodium bicarbonate can decrease the incidence of AKI after adult CPB (9) or laboratory animal models of renal injury (10).

Sodium Bicarbonate

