Treatment Arm: At the start of the surgery, the patient will receive NaHCO₃ as a continuous infusion of D5% 1/3NS + 100 meq/L NaHCO₃ + 20 meq/L KCl at maintenance IVF (solution contains ~154 meq of sodium which is equivalent to normal saline). The NaHCO₃ infusion will continue for the first 24 hours after the discontinuation of CPB. After 24 hours of receiving the NaHCO₃ infusion, the IVF administered to the patient will be the standard solutions used in the PICU at CCMC.

Control Arm: At the start of surgery, patients in the control arm will receive D5% Normal Saline + 20 meq/L KCl at maintenance IVF. After 24 hours, standard IVF, not containing NaHCO₃ or Na acetate will be administered for the duration of the PICU stay as required, determined by the clinicians primarily caring for the patient postoperatively.

Primary Outcome Measure: The efficacy of sodium bicarbonate on prevention of AKI will be tested by comparing the proportion of subjects in each of the treatment arms who progress to AKI as measured by the Pediatric Risk, Failure, Loss of Function, and End-Stage Renal Disease (pRIFLE) criteria or an absolute increase in creatinine of 0.3mg/dl.

Secondary Outcome Measures:

1. Duration of acute kidney injury
2. Cumulative fluid balance
3. Hospital and intensive care unit length of stay
4. Need for dialysis
5. Progression to pRIFLE criteria F
6. Association of NGAL as a biomarker to predict development of acute kidney injury
7. Length of mechanical ventilation
8. Change in acid-base status

II. Study Sites

Subjects will be recruited from the Cardiothoracic Surgery Division of the Cohen Children's Medical Center of New York of North Shore-LIJ Health Systems (CCMC) in New Hyde Park, New York

III. Study Subjects

Patients from CCMC come from a large geographic area with a diverse racial composition. There are currently 150 children ≤ 18 years that undergo cardiac surgery with cardiopulmonary bypass per year at CCMC. Consecutive patients scheduled for cardiac surgery who meet eligibility criteria will be invited to participate in the study.

Eligibility criteria include:

Inclusion Criteria

- 1) Subjects age ≤ 18 years
- 2) Subjects scheduled for cardiac surgery with cardiopulmonary bypass

Exclusion Criteria

- 1) Subjects with abnormal creatinine clearance (< 90 ml/min/1.7m²) as measured by the Schwartz formula

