To ensure that the chosen dose of sodium bicarbonate adequately alkalinizes the urine, we will briefly halt enrollment to blindly review urine pHs of the first 10 randomized subjects. The research nurse will be blinded to the patients' enrollment arm and the information regarding the results of the urine pH will not be available to the investigators until this interim analysis to assure appropriate blinding during the treatment of each patient. Since we have blocked randomization in groups of 10, we expect that half of the subjects will receive treatment with Sodium Bicarbonate. Therefore, we expect half of the subjects to have urine pH close to 7. If we find that urine is not adequately alkalinized, we will halt the study and submit a modification to the IRB to alter the dose of sodium bicarbonate.

VI. Study Outcomes

Demographic and Clinical Data

The medical record will be abstracted for the following variables: age, gender, diagnosis, previous surgical history, race, left ventricular ejection fraction on baseline echo, and current medications. Surgical parameters of cardio-pulmonary bypass time, ischemic time, surgical procedure, surgical complexity score, lowest temperature, use of circulatory arrest, use of cerebral perfusion, renal NIRS (measure of oxygen saturation of the renal vessels), medications administered, pH range, urine pH, surgical time, post-bypass time, estimated blood loss, and blood products administered will be measured. Cumulative fluid balance (daily Ins and Outs), hospital and intensive care unit length of stay, need for and duration of dialysis and medical complications will be recorded.

Serum NGAL is a biomarker of early AKI that often increases before serum creatinine. Specifically for this research study, serum NGAL and creatinine level will be drawn at the time of surgery and at 2, 4, 12, 24, and 48 hours.

As per routine care, creatinine will then be measured daily. pRIFLE level will be calculated on the maximum creatinine attained.

| pRIFLE Criteria | | |
|------------------------|---|---|
| | GFR | Urine Output |
| Risk | decrease by 25% | 0.5 mL/kg/h for 8 hours |
| Injury | decrease by 50% | 0.5 mL/kg/h for 16hours |
| Failure | decrease by 75% or GFR <35 | 0.3 mL/kg/h for 24 hours or anuric for 12 hours |
| Loss | Persistent failure 4 weeks | |
| End stage | End-stage renal disease (persistent failure 3 mo) | |

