2. Student’s t-test or Wilcoxon Rank Sum test for non-normally distributed variables will be used to compare values of duration of acute kidney injury, fluid balance, hospital length of stay, need for dialysis, and progression to kidney failure between groups. Pearson correlation and linear regression will be used to examine the association between duration of acute kidney injury, fluid balance, hospital length of stay, need for dialysis, and progression to kidney failure and development of AKI. Regression analysis will be adjusted for sex, age and race. Variables may be log transformed to improve the fit of the models.
3. Pearson correlation and linear regression will be used to analyze the association of NGAL with development of AKI.

II. Sample Size Estimates

Sample size estimates were calculated for the primary outcome of proportion that develop AKI in each of the two groups. Sample sizes were considered based on various effect sizes. Assuming 50% risk of AKI from our previous work, a drop from 50% AKI to:

35% would need 170 per group

30% would need 93 per group

25% would need 66 per group

20% would need 44 per group

In the literature, studies have used reductions between 20-35%. We aimed for somewhere in between. The comparison of 66 subjects in the treatment group and 66 subjects in the control group provides 80% power ($\alpha = 0.05$) to detect a difference from 0.5 in the control group to 0.25 (that is a 50% reduction in AKI) in the treatment group. nQuery software was utilized to calculate sample size.

III. Limitations

The proposed study is limited by the small sample size and heterogenous population. Given these limitations, we believe the results of the proposed study will be able to be generalized to the pediatric cardiac surgery population.

PART F. PROTECTION OF HUMAN SUBJECTS

Risk to Subjects

a. Human Subjects Involvement and Characteristics

The proposed study will involve human subjects, in particular, children and adolescents aged ≤ 18 years of age. The purpose of the study is to examine cardiac surgery in a pediatric population, therefore, other age groups are excluded from this study. Other inclusion/exclusion criteria are listed elsewhere in the protocol. This vulnerable population will be protected. Assent will be obtained from the participants and participants may withdraw from the study at any time.

b. Potential Risks

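### Death is not an outcome, so early deaths count as short stays and short ventilation; AKI duration and the staging of dialysed children are left undefined

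*Combined protocol and SAP*

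**What the plan says.** Part D, I (Overview of Study Design) gives a primary outcome based on pRIFLE "criteria or an absolute increase in creatinine of 0.3mg/dl" and eight secondary outcomes. These include "Duration of acute kidney injury", "Hospital and intensive care unit length of stay", dialysis, progression to pRIFLE F and ventilation time. Death is not among them. It is also absent from the data to be abstracted (Part D, VI, Study Outcomes) and from the analysis methods (Part E, I). Mortality is mentioned only in the background (Part B, Acute Kidney Injury): "Further, AKI was independently associated with mortality, worsening with increasing degree of AKI".

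For Aim 2, Part E, I uses a t-test or Wilcoxon test to "compare values of duration of acute kidney injury, fluid balance, hospital length of stay", dialysis and kidney failure. ICU stay and ventilation time are not named there and fall under the general two-group tests of the same section. No rule covers a child who dies.

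On severity, Part D, VI states that "pRIFLE level will be calculated on the maximum creatinine attained". The pRIFLE table beside it also has a urine-output column, whose Failure entry reads "0.3 mL/kg/h for 24 hours or anuric for 12 hours". After the 48-hour sample, "As per routine care, creatinine will then be measured daily". No text says when AKI ends, or how a dialysed child is staged.

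**The concern.** Length of stay and ventilation time are read as shorter is better. A child who dies on day 2 has a recorded stay of about 2 days, which the stated tests treat as a good result. If early deaths differ between arms, these comparisons lean towards the arm with more deaths, and no mortality comparison is planned that would show the reader why.

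Staging raises a related problem. Dialysis lowers creatinine, so a child dialysed before creatinine peaks could be staged below F on the creatinine rule. Without a definition of AKI duration, two analysts could also reach different durations for the same dialysed child. What is at stake is the reading of Aim 2, not the primary comparison.

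**Working it through.** **The plan's own figure.** The only plan number used below is 66 per arm (Part E, II). With proportions 0.50 and 0.25, two-sided alpha 0.05 and 80% power:

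- Uncorrected: n = [1.96 × √(2 × 0.375 × 0.625) + 0.8416 × √(0.25 + 0.1875)]² / 0.25² = 57.7, so 58 per group.
- With continuity correction: (57.7/4) × [1 + √(1 + 4/(57.7 × 0.25))]² = 65.4, so 66 per group.

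The stated 66 reproduces with the correction. Nothing in this point changes it.

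**How many deaths.** The documents give no mortality rate. As an assumption, 2-5% of 132 is 2.6 to 6.6 deaths. At 2% the chance of at least one death is 1 − 0.98^132 = 93%.

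**Largest effect of one death.** The win probability is the chance that a randomly chosen treated child has a longer stay than a randomly chosen control child; it is 0.50 under no effect. Each child enters 66 of the 66 × 66 between-arm comparisons. Moving one child from the longest to the shortest stay changes it by at most 66/(66 × 66) = 1/66 = 0.015.

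**Yardstick.** The null standard error is √[(66 + 66 + 1)/(12 × 66 × 66)] = √(133/52,272) = 0.050.

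| Excess early deaths in one arm | Largest shift | In null standard errors |
|---|---|---|
| 0 | 0 | 0 |
| 1 | 0.015 | 0.3 |
| 3 | 0.045 | 0.9 |
| 4 | 0.061 | 1.2 |

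Reaching p < 0.05 through this artefact alone would take about 1.96 × 0.0504 / 0.01515 = 6.5 excess deaths, each moved the full distance.

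**Illustration by simulation.** Assumptions: lognormal stay with median 7 days and log-SD 0.8, no treatment effect, 66 per arm, deaths replacing the longest stays and occurring on days 1-3.

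| Deaths, treated / control | Mean recorded stay, treated / control (days) | Win probability, raw | Win probability, deaths ranked worst |
|---|---|---|---|
| 1 / 1 | 8.9 / 8.9 | 0.50 | 0.50 |
| 4 / 1 | 7.6 / 8.9 | 0.46 | 0.50 |
| 7 / 1 | 6.8 / 8.9 | 0.42 | 0.50 |

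The raw shifts, 0.04 and 0.08, stay within the bounds 3/66 = 0.045 and 6/66 = 0.091.

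**Staging and duration.** No arithmetic applies. The staging sentence names maximum creatinine only, while the table beside it includes urine output, and nothing says which governs. Duration is listed as an outcome and tested, but has no start, end, dialysis or death rule.

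**The case against.** The case against has four parts.

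- **Dialysed children are not hidden.** Dialysis is a secondary outcome in its own right, and its duration is recorded. This stands, and limits the staging point to the stage and duration assigned to those children.
- **Deaths are not invisible.** Adverse events are monitored, and an independent reviewer looks at the study at one quarter, one half and three quarters of enrolment (Part H). This stands for safety oversight, but it does not give a planned comparison by arm or a rule for length of stay.
- **The effect is small.** One excess death is 0.3 of a standard error, and an excess of four cannot occur if there are only three deaths. Withdrawal of children who need ECMO or LVAD may also remove some of the sickest. This stands on size. Any lean still favours the arm with more early deaths.
- **The primary endpoint is robust.** Its threshold is low, sampling is frequent, and a creatinine maximum already reached is not erased by later dialysis. This stands.

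A reader might infer that severity and duration rest on creatinine alone. The documents do not support that: the table has a urine-output route to Failure, and duration is undefined rather than tied to creatinine. The urine-output route is not a sure safeguard either, because Part D, V.d has urine flow actively supported to a target. A reader might also infer that an AKI duration cut off at 2 days by death looks favourable. Part D, V.c says that AKI lasts under 48 hours in 75% of patients, so 2 days is not short on that outcome.

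**Conclusion.** The point holds in a limited form. Death is not an outcome, and under the stated tests an early death enters hospital stay, ICU stay and ventilation time as a short value. The resulting bias is at most 1.5 percentage points of win probability per excess death, against a standard error of 5 points, and is nil when deaths are balanced. The assumed 2-5% mortality sets only the plausible count of deaths; the bound per death needs no mortality rate.

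It would go too far to say that the Aim 2 conclusions are likely to be reversed: four excess deaths amount to about 1.2 standard errors. It would also go too far to say that dialysed children would generally be counted as free of AKI, since they would have to be dialysed before meeting any AKI criterion. What remains on the renal side is an unclear staging rule and an undefined duration. The primary result and the sample size are not materially affected, so this is an inexpensive improvement to the secondary analyses.

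**What to change.** Make these changes before unblinding:

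1. Add all-cause death, in hospital and to day 30, as an outcome reported by arm. Add vital status to the abstraction list. The day-30 visit helps, but non-attendance does not establish whether a child is alive, so vital status needs its own entry.
2. Compare hospital stay, ICU stay and ventilation time by Wilcoxon test with deaths given the worst rank, and show medians in survivors alongside.
3. For progression to pRIFLE F, count children who receive dialysis for kidney dysfunction as F, and record the indication for dialysis.
4. Define the start and end of AKI for the duration outcome, and do not count AKI as resolved while dialysis continues.
5. State whether urine output counts in pRIFLE staging.
6. Leave the primary endpoint definition unchanged.

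The cost is mainly analysis-plan wording plus two added data items, vital status and dialysis indication; dialysis need and duration are already recorded. A worst-rank comparison reads less directly than a difference in days, which is why the survivor medians should sit beside it. No more subjects are needed.

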Items marked in **RED** indicate procedures being done specifically for the research study. Blood draws at 4 hours post-operatively are standard practice for certain patients, based on complexity of the surgical procedure, and will be done for

research purposes on some patients who had less complex surgeries. All other procedures represent standard practice for all patients undergoing cardiopulmonary bypass for correction of congenital heart lesions.

a. Screening Visit

Eligibility and demographic data will be collected on all children scheduled for cardiac surgery with cardiopulmonary bypass during the study interval. Subject and disease characteristics will be recorded for all ineligible subjects and those declining participation. Potential subjects will be screened using the protocol inclusion and exclusion criteria. Pre-surgical testing laboratory data, collected as part of standard care, will be reviewed. Study subjects who meet the eligibility criteria will be asked to participate in the study in person by physicians known to them in clinic or in the hospital. Parental/guardian permission (informed consent) and, if applicable, child assent, will be obtained prior to any study related procedures being performed.

b. Perioperative Management

As part of their standard care, subjects will have baseline height, weight, comprehensive metabolic panel, complete blood count and serum pH done on the day of surgery at the time of IV and arterial line insertion. Subjects will then be randomized into one of the treatment groups and will receive the intervention at the start of surgery.

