Clinical practices associated with cardiac surgery will not be modified for the purpose of the study and standard of care will be given to all patients. Intra-operative fluid management will be left to the discretion of the anesthesiologist and will be documented. Intra-operative serum pH will be monitored and subjects may receive sodium bicarbonate boluses regardless of treatment group as standard of care if needed (this is done infrequently). As part of the standard practice, all subjects will receive Ancef at the time of surgery and will be continued for three doses (vancomycin is used in cases of allergy). A foley catheter will be placed and urine output will be recorded. Any pre-operative electrolyte disturbances (i.e. hypokalemia, hypernatremia, hypocalcemia and acidosis) will be corrected prior to administration of NaHCO₃. Serum and serum electrolytes will be done during surgery at the discretion of anesthesia and bypass team as per protocol. Electrolyte abnormalities will be treated by the anesthesiologist and will be documented.

c. Intervention

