Creatinine clearance will be estimated by the Schwartz formula ($k \times ht \text{ (cm)} / \text{creatinine}$; $k = 0.4$ premature, $k = 0.55$ females and pre-pubertal males <13 , $k = 0.7$ pubertal males). NGAL will be measured by enzyme-linked immunosorbent assay. Urine pH will be measured at 2, 4, 12, 24 hours post surgery, and as described above, the investigators will be blinded to these results. Serum pH and electrolytes will be measured at 2, 4, 12, 24 hours. NGAL and urine pH will be measured specifically for the purpose of performing this research study. Serum pH is routinely measured as standard practice in post-operative cardiothoracic surgery patients during surgery, and at hours 2, 12, and 24 hours post-operatively.

PART E. Statistical Issues

I. Statistical Analysis

Statistical analyses will be done using SPSS 18.0 (SPSS Inc., Chicago, IL) statistical package. A two-tailed p-value < 0.05 is the criterion for statistical significance. Intention to treat analysis will be done. Descriptive statistics will be used to characterize outcome measures in subjects. Means, standard deviations, 95% confidence intervals, medians, and minimum and maximum values will be tabulated and reported for all continuous variables. Frequency counts and percentages will be used for categorical variables. The distributions of each outcome will be examined for normality. Baseline demographic and clinical data of the two arms will be examined. Differences in means in the treatment group will be compared to the control group using Student’s t-test, or the Wilcoxon Rank Sum test if the data are not normally distributed. Differences in proportions will be assessed using the chi-square test.

Specific Aims:

1. To analyze the primary outcome, chi-square will be conducted to compare the proportion of subjects who develop AKI by pRIFLE criteria in the two groups.

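### Secondary outcome 8, change in acid-base status, has no assigned analysis; one repeated-measures model adjusted for the pre-operative pH should replace the default unadjusted test

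*Combined protocol and SAP*

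**What the plan says.** The eighth and last secondary outcome in Part D.I is "Change in acid-base status". No variable (serum pH, bicarbonate or base deficit), reference time or summary measure is attached to it.

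The data are there. Part D.V.b has "serum pH done on the day of surgery at the time of IV and arterial line insertion", and randomization follows. Part D.VI adds: "Serum pH and electrolytes will be measured at 2, 4, 12, 24 hours". The study procedures table in Part D.V appears to carry serum pH on to 48 hours, although its columns are hard to align in the text available.

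Part E.I gives a general rule: "Differences in means in the treatment group will be compared to the control group using" Student's t-test, or the Wilcoxon rank-sum test for non-normal data. The entry for Aim 2 applies those tests to "compare values of duration of acute kidney injury, fluid balance, hospital length of stay, need for dialysis, and progression to kidney failure between groups"; acid-base status is not in that list. The only covariate adjustment is "Regression analysis will be adjusted for sex, age and race", and that regression relates outcomes to the development of AKI. It does not compare the arms.

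**The concern.** An outcome worded as a change, with a baseline value and at least four later values, can be analysed in several ways: the change to one time, the change at each time, the post-operative value alone, or an average. The plan chooses none of them, and the default test uses no covariate. Two things follow.

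- **Precision.** A pre-randomization measurement of the same quantity is the natural covariate, and it goes unused as one. If the test is run on change scores and the baseline correlation is low, subtracting baseline can add noise. Low correlation is plausible here: Part D.V.b has pre-operative acidosis corrected before study drug, and Part D.V.c has base deficits corrected during bypass in both arms.
- **Choice after the fact.** With no time or summary fixed, the reported comparison could be selected once the data are seen.

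Part C gives raising blood pH as part of the drug's action, so this outcome helps to interpret a null AKI result: did the infusion move systemic acid-base balance at all?

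**Working it through.** **The plan's own figure.** No SD, effect size or power is stated for acid-base status. The only sample-size figure is for AKI (Part E.II): 50% vs 25%, two-sided 0.05, 80% power, 66 per group. The uncorrected two-proportion formula gives

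n' = [1.960·√(2·0.375·0.625) + 0.842·√(0.25 + 0.1875)]² / 0.25² ≈ 57.7, so 58.

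The continuity-corrected formula gives (n'/4)·[1 + √(1 + 4/(0.25·n'))]² ≈ 65.4, so 66. The stated figure reproduces with the correction, and nothing below touches it.

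**Inputs for this outcome.** From the documents: 1:1 allocation, 66 per arm, two-sided 0.05. Assumed: r, the within-arm correlation of pre- and post-operative pH, and k, the pre-operative SD divided by the post-operative SD. Neither is in the documents, so ranges are shown.

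**Variances at one sampling time, with post-operative variance set to 1**
- post-operative value alone: 1
- change score: 1 + k² − 2kr, which is 2(1 − r) when k = 1
- baseline-adjusted (ANCOVA): 1 − r²

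Change score minus ANCOVA is (k − r)². Post-only minus ANCOVA is r². Neither can be negative.

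**Equal SDs (k = 1).** The detectable difference is in post-operative SD units at 66 per arm and 80% power, by normal approximation: (1.960 + 0.842)·√(2/66)·√variance. For the post-operative value alone it is 0.488.

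| r | Change-score variance | ANCOVA variance | Saving vs change, (1 − r)/2 | Saving vs post-only, r² | Detectable: change | Detectable: ANCOVA |
|---|---|---|---|---|---|---|
| 0.2 | 1.60 | 0.96 | 40% | 4% | 0.617 | 0.478 |
| 0.3 | 1.40 | 0.91 | 35% | 9% | 0.577 | 0.465 |
| 0.5 | 1.00 | 0.75 | 25% | 25% | 0.488 | 0.422 |
| 0.7 | 0.60 | 0.51 | 15% | 49% | 0.378 | 0.348 |

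The two savings move in opposite directions as r rises, so any single percentage has to name its comparator.

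**Smaller baseline spread (k = 0.5, an illustration).** Change-score variance is 1.25 − r.
- r = 0.2: 1.05 vs 0.96, saving 9%
- r = 0.3: 0.95 vs 0.91, saving 4%
- r = 0.5: 0.75 vs 0.75, saving 0%

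The correlation below which subtracting baseline adds noise is k/2: 0.5 when k = 1, and 0.25 when k = 0.5.

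**Cost.** One covariate multiplies the variance by about 1 + 1/(132 − 4) = 1.008, or 0.8%.

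**The case against.** The strongest reply is that the plan does not commit the error that a critic would like to charge it with. A reader might infer that raw change scores will be tested separately at 2, 4, 12 and 24 hours. Neither step is written. The t-test sentence is generic, follows directly on the sentence about baseline data, and reaches this outcome only because nothing else does. One change to 24 hours would fit the text equally well.

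For the same reason, a familywise false-positive rate of 1 − 0.95⁴ ≈ 19% should not be charged to the plan. It needs four separate tests, which are not planned, and independence, which is implausible for serial pH in one child within a day.

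A reader might also take a 25% to 40% variance reduction as what adjustment delivers. That range holds only against change scores, with equal SDs and r between 0.5 and 0.2. If r really is low, the covariate itself does little. At r = 0.3 the variance falls from 1.40 to 0.91. Of that 0.49, 0.40 comes from not subtracting baseline and only 0.09 from adjusting. With a smaller baseline spread, most of the gain over change scores goes too.

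Finally, the hypothesis in Part B concerns urinary alkalization, and Part D.V.g checks the dose through urine pH in the first 10 subjects. Serum acid-base status is the last of eight secondary outcomes.

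All of this stands as a limit on the size of the point. It does not supply an analysis for the outcome, and it does not favour an unadjusted one: the inequalities above hold for every r and k.

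**Conclusion.** The point holds in a limited form. The outcome has no assigned analysis, the default is an unadjusted two-group test, and a better method is available from data already being collected.

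Adjustment is never worse than either alternative beyond about 0.8% of variance. The gain is uncertain: with equal SDs and r from 0.2 to 0.7 it is 40% to 15% against a change score and 4% to 49% against the post-operative value alone, and it can be near zero against a change score when baseline spread is much smaller. These figures are for one sampling time and rest on assumed r and k; no fixed gain should be promised.

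This is a low-priority improvement. It does not alter the AKI analysis or the 66 per group.

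**What to change.** In Part E.I, add a short paragraph for secondary outcome 8:

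- **Variable and times.** Serum pH at the scheduled 2, 4, 12 and 24 hour samples. Reconcile Part D.VI with the procedures table, which appears to add 48 hours, and state whether that sample enters the model. It would fall after the infusion period described in Part D.V.c.
- **Model.** One repeated-measures model with arm, time, arm-by-time and the pre-operative pH as covariate. Letting the pre-operative coefficient vary by time keeps the no-loss argument valid at each sample.
- **Inference.** One overall test for arm, defined in advance (for example, the arm difference averaged equally over the scheduled times), with adjusted between-arm differences and 95% CIs at each time as description.
- **Bicarbonate.** If analysed, treat it as supportive, so that it does not create a second main test.
- **Missing values.** State a rule for a missing pre-operative pH and for missed later samples.

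The cost is SAP wording only. No new samples are needed, and the planned software can fit the model. The choice should be fixed before unblinding.
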